5.1.1 Oscillometry

Oscillometry is a non-invasive technique for assessing lung function, as it requires only 45-60 seconds of tidal breathing to measure the mechanical properties of the respiratory system. This makes the measurement suitable for patients of all ages and with severe respiratory conditions. It also reduces the number of errors as compared to other methods (e.g., spirometry).

Oscillometry can be used to evaluate airway resistance, reactance, and compliance, insights that are challenging to obtain with other methods. This quality makes oscillometry especially sensitive for obstructive diseases like asthma and COPD, and correlations with physiological small airways dysfunction have also been shown. 14–16

The Ambulatory Lung Diagnosis System (ALDS), manufactured by Lothar Medtec, can be used to perform oscillometry and spirometry (Figure 5). The ALDS follows the European Respiratory Society (ERS) technical standards for measurement and reporting of oscillometry.

[figure not shown]

Figure 53. Oscillometry and spirometry performed with the ALDS system. A) Schematic overview of oscillometry process and decision support by the ALDS. B) Example of a report generated by the ALDS.

The measurement is performed using approximately 45-60 seconds of tidal breathing. Three measurements of 15 seconds will be performed, during which the patient will calmly breathe in and out while wearing a nose clip. This requires no specific training or effort from patients. The HCP can be trained within 15 minutes on how to perform the measurement and the requirements for accurate measurement. The ALDS has built-in quality control measures and provides feedback if quality is not sufficient.

Contingent on the results of the oscillometry testing, reversibility testing can also be conducted using the ALDS device, in addition to standard oscillometry measurements. When the ALDS suggests execution of a reversibility test, this is performed according to the ERS guideline with use of 400 μ g Salbutamol as the bronchodilator. ¹⁷ If required, post-bronchodilator spirometry can also be performed using the ALDS device after training of HCPs.

The BiaB-app and the ALDS are integrated seamlessly. The complete ALDS output will be integrated in the BiaB-report. The resulting physiological interpretation, combined with the clinical BiaB-decision tree interpretation will be presented in the BiaB-report.

5.1.2 Electrocardiogram

A primary method of evaluating breathlessness, adjunct to pulmonary tests, is through an electrocardiogram (ECG). Breathlessness could well be a symptom of cardiovascular conditions, particularly heart failure.¹⁸

The CardioSecur Pro (Personal MedSystems GmbH, Frankfurt, Germany) will be used for ECG measurement as a diagnostic tool for cardiologic causes of breathlessness. The CardioSecur Pro is a 12+ leads ECG technology that uses 4 electrodes, which are placed on the thorax. This test is commonly used in diagnostic procedures in primary care. This technology is based upon the EASI lead standard and was clinically proven. There is >99% agreement between the CardioSecur ECG and standard ECG for detection of myocardial ischemia.

The PMCardio algorithm (Powerful Medical, London, UK) is an AI powered diagnostic medical device for ECG assessments. The diagnostic performance of the device was examined in a study that encompassed more than 932,711 ECGs. High sensitivity, specificity and positive/negative

predictive values were demonstrated across all diagnostic categories. The findings indicate strong potential for the interpretation to enhance diagnostics.^{21,22}

HCPs will retain the opportunity to use their own ECG device and run this through the PMCardio algorithm. PMCardio has the ability to interpret ECG results from all devices, allowing the HCP to be able to use their own ECG device. We have considered this option, because of health insurance reimbursements within the practices in primary care. Beside this, HCPs are often familiar with the equipment they have in their practice.

The PMCardio algorithm, a software application for interpretation of ECG results, will be integrated in the BiaB-app. The ECG interpretation, combined with the clinical BiaB-decision tree interpretation will be presented in the BiaB-report.

5.1.3 N-terminal pro-B-type Natriuretic Peptide (NT-proBNP)

B-type Natriuretic Peptide (BNP) is secreted by cardiomyocytes in response to any damage to the cardiovascular system. BNP and NT-proBNP in blood have been known as the gold standard, recommended by the American Heart Association and the American College of Cardiology, to identify heart failure (HF).²³ Of the two analytes, NT-ProBNP has a longer half-life and more consistent blood concentration.

The BiaB-box will include the LumiraDx point-of-care device (LumiraDx Ltd, London, UK) for quantitative assessment of NT-proBNP levels for point-of-care diagnostics of HF. This test is commonly used in diagnostic procedures in primary care. The measurement will be performed in approximately 20 μ L of capillary blood obtained by a standard finger stick. HCPs will be instructed about use of the device but do not require training for the finger stick. For automated interpretation of quantitative values, cut-off values, depending on age, according to the paper by Gaggin et al. will be used.²⁴

Results generated by the LumiraDx will be retrieved by the BiaB-app automatically. The BiaB-app will interpret the measurement according to guidelines taking into account the relevant dependencies. Results will be incorporated into the BiaB-report.

5.1.4 YEARS criteria and D-dimer test

Sudden breathlessness may be a sign of pulmonary embolism (PE), which requires urgent care. Therefore, it is important to investigate further when PE is suspected. This is a common method in primary care. This can be done using the YEARS criteria, which are derived from the most predictive items of the previously used Wells score. Compared to the Wells scores, with fixed D-dimer cut off values, the YEARS algorithm reduces the use of a CT pulmonary angiogram (CTPA) by 14%. The YEARS algorithm has been shown to rule out PE (only 0.43% with a symptomatic venous thromboembolism (VTE) during 3 months follow-up) and has been incorporated in international guidelines. The score derived from the YEARS algorithm dictates interpretation of the D-dimer test. D-Dimer, a fibrin degradation product, is a thrombotic biomarker used to exclude PE.²⁷

In cases of suspicion of a PE, the YEARS criteria (Appendix A) and a D-dimer test will be advised in the BiaB-app. D-dimer can be tested on the same LumiraDx point-of-care device used to measure NT-proBNP levels with a different test cartridge. The measurement will be performed in approximately 10 μ L of capillary blood obtained by a standard finger stick. PE can be ruled out if none of the YEARS items are applicable and D-dimer <1000 ng, or, if 1-3 YEARS items are applicable and D-dimer is <500 ng (Figure 6). 25,26

[figure not shown]

Figure 6. Decision tree for YEARS algorithm with binary d-dimer cut off values, adapted from Van der Pol 2019²⁸.

Results generated by the LumiraDx will be retrieved by the BiaB-app automatically. The BiaB-app will interpret the measurement according to guidelines taking into account the relevant dependencies. Results will be incorporated into the BiaB-report.

5.1.5 Patient Health Questionnaire-4 (PHQ-4)

As mentioned in the introduction, anxiety and depression are two of the primary underlying conditions contributing to breathlessness. Contributing to the necessary integrated approach needed for defining the cause of breathlessness, the PHQ-4 is incorporated into BiaB. The PHQ-4 is a brief self-report questionnaire that consists of a 2-item anxiety scale (GAD-2) and a 2-item depression scale (PHQ-2)⁶ (Appendix B). This tool was found to be able to measure anxiety and depression reliably and validly in the general population.²⁹

The GAD-2 is the short version of the 7-item Generalized Anxiety Disorder Scale (GAD-7), which was found to accurately diagnose the four most common anxiety disorders. The PHQ-2 focuses on depressed mood and loss of interest, thereby representing the DSM-5 diagnostic core criteria. A total score \geq 3 for the first 2 questions will be used as cut-off to suggest anxiety and a total score \geq 3 for the last 2 questions will be taken as cut-off to suggest depression.²⁹

The patient fills out the PHQ-4 questionnaire, which is incorporated into the BiaB-app. The BiaB-app will interpret the questionnaire according to guidelines. Results will be incorporated into the BiaB-report.

5.1.6 Oxygen saturation measurement

The common causes of breathlessness can be divided amongst a cardiac, pulmonary, mental health or other category. Once cardiac, pulmonary, or mental health causations have been ruled out, focus on the 'other' category is necessary. Causes listed in this category are obesity, physical deconditioning, anaemia or long COVID. Unexplained reduction of peripheral capillary oxygen saturaitoin (SpO_2) or low SpO_2 levels during minimal activity can indicate sever acute breathlessness which upon review of the HCP can merit specialist assessment. Pulse oximeter is a non-invasive measurement of SpO_2 . This test is commonly used in diagnostic procedures in primary care. As per guidelines, a cut-off value of $\geq 95\%$ will be used for interpretation of the result. Results will be incorporated into the BiaB-report.

5.1.7 Decision-tree for interpretation of test results

A decision-tree will be used for clinical decision support. This decision-tree combines all findings from the several assessments performed. The current version of the decision-tree is based on the pilot project (unpublished) and is now further optimized with the additional tests and new findings.

6. Methods

6.1 Study parameters/endpoints

For all study endpoints, the analysed population will include patients from usual care and the BiaB intervention period.

6.1.1 Primary study endpoint

The primary endpoint is days between presentation with or consultation for breathlessness and a diagnosis causing the breathlessness (usual care group versus BiaB intervention group).

Required variables:

- Date of presentation with breathlessness,
- Date of first consultation for breathlessness,
- Date of diagnosis, and
- Type of diagnosis.

Strategy: Data will be retrieved during patient consultation (presentation and consultation for breathlessness) and periodically (up to 12 months, to account for referral waiting times) from healthcare professional (HCP) reporting (date and type of diagnosis). The exact date of presentation with breathlessness, consultation and diagnosis will be recorded. If exact date of presentation is unknown, it will be set to [01/MM/YYYY], where MM is the month where symptoms started. If duration of presentation is >1 month and start date is unknown, it will be set to either [01/01/YYYY] or [01/07/YYYY] (whichever is most accurate). Date of diagnosis is defined as date of recorded diagnosis related to breathlessness by any HCP (either reported by

HCP or noted in referral documentation) or start of treatment related to breathlessness. If multiple diagnoses are recorded, all will be collected, and the first diagnosis is used to determine time to diagnosis. Patients with missing data will be censored. In countries where a preliminary diagnosis is entered int the medical records to make prescription of medication possible before diagnostic tests are performed, the date of diagnosis will be validated by the HCP to ensure final clinical diagnosis date.

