6.1.2 Secondary study endpoints

6.1.2.1 First secondary endpoint

The first secondary endpoint is the number of new diagnoses of COPD and heart disease (CVD) in patients (usual care group versus BiaB intervention group).

Required variables:

- The number of newly diagnosed patients
- The number of new diagnoses
- The number of diagnoses per patient
- The number of patients presenting with breathlessness
- The type of diagnosis

Strategy: Data will be retrieved periodically (up to 12 months, to account for referral waiting times) from HCP reported outcomes (date and type of diagnosis). All types of diagnosis will be recorded. For determining the secondary endpoint, type of diagnosis will be categorized as either heart, respiratory, psychological, and other. In case no diagnosis is reported, this will be reported as late diagnosis. If multiple diagnoses are recorded, all will count towards the endpoint. In countries where a preliminary diagnosis is entered int the medical records to make prescription of medication possible before diagnostic tests are performed, the date of diagnosis will be validated by the HCP to ensure final clinical diagnosis date.

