6.1.2.2 Second secondary endpoint

The second secondary endpoint is to demonstrate the usability and efficiency of BiaB.

Required variables:

- Number of lung function tests
- Number of ECG measurements
- Number of referrals to specialist
- Type of referral to specialist
- Number of acute hospital admissions
- Duration of hospital admission
- Number of emergency room visits

Strategy: Data will be retrieved from HCP reported outcomes. Anonymous data pertaining to the total number of lung function tests, ECG measurements and referrals are not limited to patients participating in the BiaB study.

- Clinical outcomes
 - o Contents of BiaB report
 - a) Test results
 - b) Outcomes
 - c) Advice
 - d) Diagnosis
 - o Change in breathlessness³⁰
 - Number of cardiopulmonary events ³¹
 - a) COPD exacerbation
 - b) Myocardial infarction
 - c) Stroke
 - d) Heart failure decompensation
 - e) Arrhythmia
 - f) Death due to any of these events
 - o Change in prescribed medication

Performed procedures (at visit and follow-up/referral)

Strategy: Change in breathlessness will be measured over time (0, 3, 6, 9, 12 months) as a patient reported outcome using the numeric rating scale (NRS)^{32,33}. The number of cardiopulmonary events will be recorded at 3, 6, 9, 12 months, reported by HCP. Cardiopulmonary events are defined as COPD exacerbation, myocardial infarction, stroke, heart failure hospitalization, arrhythmia, and death due to any of these events³¹. COPD exacerbations are identified through use of oral corticosteroids irrespective of antibiotics use. Arrhythmia is defined as atrial and ventricular tachyarrhythmia. Change in prescribed medication will be determined by comparing medication prescribed before consultation for breathlessness to prescribed medication after consultation for breathlessness as reported by HCP. Data about procedures performed during visit, follow-up and referral will be collected through HCP reported outcomes.

BiaB use

- Number of times BiaB is started
- Number of unique generated reports
- State of generated reports
- Number of times BiaB advice is followed
- Prescribed treatment or referrals
- Performed procedures

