6.3 Study procedures

Data collection will take place during the BiaB visit, retrospectively, and after the visit during the follow-up period. See the Schedule of Assessments with an overview of all performed procedures (Table 1).

Table 1. Schedule of assessments for usual care and BiaB intervention period.

Schedule of assessments (usual care period)								
Visit	Visit 01	Visit 11	Follow up 1	Follow up 2	Follow up 3	Follow up 4		
Time (months)	0	0	3 (+14 days)	6 (+14 days)	9 (+14days)	12 (+14 days)		
Invitation + Informed consent	Invitation + Informed consent							
Invitation and informed consent provided	Χ							
Informed consent procedure		Х						
Patient reported outcomes (electronic) ²								
WPAI		Х	X	Х	Χ	Х		
EQ-5D-5L		Х	Х	Х	Χ	Х		
Healthcare utilization		Х	X	Х	Х	Х		
NRS dyspnea		Х	Х	Х	Х	Х		
Diagnosis questionnaire		Х	Χ	Χ	Χ	Х		

Schedule of assessments (BiaB intervention period)							
Visit	Visit 01	Visit 1 ¹	Follow up 1	Follow up 2	Follow up 3	Follow up 4	
Time (months)	0	0	3 (+14 days)	6 (+14 days)	9 (+14days)	12 (+14 days)	
Invitation + Informed consent							
Invitation and informed consent provided	Χ						
Informed consent procedure		Х					
BiaB visit							
Patient characteristics		Х					
YEARS questionnaire + D-dimer test (optional)		Х					
SpO2 measurement		Χ					
NT-proBNP test		Х					
PHQ-4 questionnaire		Х					
ECG		Х					
Oscillometry		Χ					
Patient reported outcomes (electronic) ²							
WPAI		Х	Χ	Χ	Χ	Х	
EQ-5D-5L		Х	Х	Х	Χ	Х	
Healthcare utilization		Х	Х	Х	Х	Х	
NRS dyspnea		Х	Χ	Х	Х	Χ	
Diagnosis questionnaire		Х	Χ	Х	Х	Χ	

1 VO and V1 can be at the same moment if regulations allow
2 (electronic) patient reported outcome ((e)PRO), see section 6.3.2

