6.3.2 Patient reported outcomes

During the follow-up period, every three months for up to a year, patients will be asked to fill out questionnaires (WPAI, EQ-5D-5L, healthcare use, numeric rating scale (NRS), and diagnosis)

(Appendix C-F). The preference for the study is to make use of electronic questionnaires. Patients can receive the questionnaires by email or will be invited at the study site. Patients which are hesitant or unable to complete information using electronic questionnaires will be provided with paper copies. Data will then be entered into the eCRF using double data entry.

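### Diagnoses made outside the practice may be captured less completely in usual care, and the patient questionnaires that could reveal this have no role in the endpoints

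*Protocol*

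**What the plan says.** **Sources for the endpoints.** Section 6.1.1 retrieves the outcome "from healthcare professional (HCP) reporting (date and type of diagnosis") for up to 12 months. The definition that follows is wide: "Date of diagnosis is defined as date of recorded diagnosis related to breathlessness by any HCP", whether reported by the "HCP or noted in referral documentation) or start of treatment related to breathlessness". Where several diagnoses are recorded, the first one sets the time. On gaps it says "Patients with missing data will be censored". Section 6.1.2.1 also uses HCP-reported outcomes for new COPD and heart disease, and adds "In case no diagnosis is reported, this will be reported as late diagnosis". For tests, referrals, acute admissions and emergency visits, section 6.1.2.2 states "Data will be retrieved from HCP reported outcomes".

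**Other routes.** Section 3 provides for extraction from practice electronic records, and section 6.3.3 for quarterly HCP reports. Neither is restricted to one period. Section 6.3.4 lets a specialist enter the diagnosis directly, through a link and QR code printed on the BiaB report.

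**Patient reports.** Section 6.3.2 says that every three months "patients will be asked to fill out questionnaires (WPAI, EQ-5D-5L, healthcare use, numeric rating scale (NRS), and diagnosis"). Table 1 in section 6.3 lists the "Diagnosis questionnaire" and the healthcare-use questionnaire at months 0, 3, 6, 9 and 12 in both the usual-care and the BiaB schedule. Section 6.1 gives neither a role. In the economic analysis it names only the WPAI and EQ-5D-5L.

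**The concern.** The primary endpoint is a time to event, and the event is a piece of information that has to be passed on. The protocol expects some diagnoses to be made after referral, because it follows patients for 12 months to allow for referral waiting times. If such a diagnosis is never fed back, the data look the same as for a patient who was never diagnosed.

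Equal loss in the two groups would create no difference where none exists. The risk lies in unequal loss, and the protocol contains one feature that points that way: the specialist's direct entry route hangs on a document that only BiaB patients have. Better capture under BiaB would shorten the observed time to diagnosis and raise the count of new COPD and heart disease in that group, with no change in care. A source independent of the practice and scheduled identically in both periods is already planned, but nothing is done with it.

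**Working it through.** **1. Which sources exist in which period**

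| Source | Section | Usual care | BiaB | Needs feedback to the practice |
|---|---|---|---|---|
| Quarterly HCP report | 6.3.3 | yes | yes | yes |
| Practice record extraction | 3 | yes | yes | yes |
| Referral documentation, treatment start | 6.1.1 | yes | yes | yes |
| Specialist questionnaire | 6.3.4 | no | yes | no |
| Patient diagnosis and healthcare-use questionnaires | 6.3, 6.3.2 | yes, no endpoint role | yes, no endpoint role | no |

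The specialist questionnaire is the only row that differs by period. The patient questionnaires are the only source that is both common to the two periods and independent of the practice.

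**2. Who is affected**

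The first recorded diagnosis or treatment start sets the time. A missed specialist letter therefore matters to the primary endpoint only if the patient had neither before the referral and nothing reaches the practice within 12 months. Such a patient stays without an event up to the censoring date.

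**3. Size, as an illustration**

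The protocol gives no rate of missed diagnoses, so there is no figure of its own to reproduce. Inputs:

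- Mean time in usual care: 70 days, with a 14-day reduction to 56 days under BiaB (assumptions in section 4.3).
- Summary measure: the median (section 8.1.2).
- Assumed here: exponential times; a share u of diagnoses is never captured, at random with respect to time; those patients remain at risk.

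The observed event curve is (1 − u) × (1 − exp(−t/mean)). Setting it to 0.5 gives

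observed median = −mean × ln(1 − 0.5/(1 − u)).

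For mean 70:

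- u = 0: 70 × ln 2 = 48.5 days
- u = 4%: −70 × ln(1 − 0.5/0.96) = 51.5 days
- u = 5%: −70 × ln(1 − 0.5/0.95) = 52.3 days
- u = 10%: −70 × ln(1 − 0.5/0.90) = 56.8 days

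| Missed, usual care / BiaB | Difference in medians, no true effect (70 vs 70) | Difference in medians, true effect as planned (70 vs 56) |
|---|---|---|
| 0% / 0% | 0 | 9.7 |
| 10% / 10% | 0 | 11.4 |
| 4% / 0% | 51.5 − 48.5 = 3.0 | 51.5 − 38.8 = 12.7 |
| 10% / 5% | 56.8 − 52.3 = 4.5 | 14.9 |
| 10% / 0% | 8.2 | 17.9 |

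Equal loss leaves a null result null. Unequal loss creates an apparent benefit of a few days.

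These figures probably lean high. The calculation spreads missed diagnoses evenly over time, whereas referred patients are likely to be diagnosed late. A missed diagnosis that truly falls after the median hardly moves the median.

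**The case against.** **The endpoint is broader than the practice's own report.** Any HCP's diagnosis, referral documentation and start of treatment all count, and quarterly HCP reporting and record extraction apply to both periods. This stands. A reader might infer that outside diagnoses are ignored or treated as not made, and the text does not support that. A documented specialist diagnosis qualifies, and missing data are to be censored. The wording about late diagnosis belongs to the first secondary endpoint only. That an uncaptured diagnosis contributes no event is an inference, though a fair one.

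**The direction is not certain.** BiaB could also prompt more referrals, and so more diagnoses that depend on feedback. This stands too: the specialist link points towards an advantage for BiaB, but the net effect is unknown.

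**The size is assumed.** A more alarming figure is easy to produce. If 4% of usual-care patients are moved from 70 to 365 days, the 12-month mean shifts by 0.04 × (365 − 70) = 11.8 days, or 84% of the 14-day effect. The protocol does not plan a restricted mean. That calculation also places every missed patient at the overall average of 70 days and ignores earlier diagnoses or treatment starts. On the median the same 4% gives about 3 days.

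**The questionnaire may not hold the answer.** Appendix G is not available, so it cannot be said that the trial already has the type or date of the missed diagnosis. This is a reason to use the questionnaire only as a trigger.

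**This is data management.** Requiring a clinician's record is a defensible choice, and nothing prevents the monitoring plan from adding a cross-check. But section 8 only requires the SAP to be final before database lock. A check of this kind has to run during follow-up, so it cannot be left to the SAP.

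**Conclusion.** The point holds in a limited form. Capture of diagnoses made outside the practice depends on feedback to the practice, apart from a specialist route that only BiaB patients have. The patient diagnosis and healthcare-use questionnaires are collected on the same schedule in both periods and have no stated use in section 6.1. Loss could therefore be greater in usual care and favour BiaB.

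The size cannot be known from the protocol. With exponential times of mean 70 days, random loss and no true effect, the apparent benefit is about 3 days for 4% against 0% and about 4.5 days for 10% against 5%. It is zero for equal loss. The documents establish neither that the bias is present nor that it approaches the 14-day effect. This is an optional improvement, not a defect that undermines the primary analysis.

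**What to change.** Add to sections 6.1.1 and 6.1.2.1: at each quarterly contact, a diagnosis on the patient questionnaire that is absent from the HCP data raises a query in the EDC system, by the same rule in both periods. The practice confirms or refutes it from source documents and enters the date on which the diagnosis was made. Only confirmed diagnoses count. Add to section 6.1.2.2 the same use of the healthcare-use questionnaire for acute admissions and emergency visits.

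The cost is one query rule, a few sentences and some practice time. The upper bound is 900 patients × 4 follow-ups = 3,600 automatic comparisons, of which only the mismatches need an answer. The check works only for patients who return questionnaires, so it reduces unequal capture but does not remove it.
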